3.2 Primary Study Endpoints

Objective: Investigate the feasibility of a clinical trial administering ionizing radiation with concurrent CR for the treatment of breast cancer. True adherence will be defined as a successful reduction of 25% of total calories based on diet journals in at least 80% of the logged events. Acute skin toxicity as defined by the National Cancer Institute Common Toxicity Criteria (NCI CTCv.4 for skin reaction, pain and the occurrence of moist desquamation) will be followed to ensure noninferiority as compared with historical controls.

To obtain baseline caloric intake, patients will keep food diaries for 7 to 10 days. On the basis of these diaries, a caloric intake will be computed for each day. Each patient's baseline (pre-diet) caloric intake will then be the average caloric intake in this pre-diet phase. The target caloric intake during the diet phase will be set to 75% of this baseline average (25% restriction).

The diet phase will be defined as the entire length that a patient is on the calorically restricted diet. This includes a minimum of 2 weeks before the patient starts radiation therapy and a minimum of 2 weeks after completion of radiation therapy. This will guarantee that patients have been on the diet for a minimum of 10 weeks, regardless of whether or not the patients have exceeded the 10 weeks. In the diet phase, patients will also keep daily food diaries. An average daily caloric intake will be computed for each week. If that daily average is more than the restricted target or if there are fewer than 4 diaries during any given week, that week will be considered as non-adherent. Overall adherence with the diet intervention over the entire study will be defined as at least 80% of all logged events meeting the diet restriction target.

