6.2.3 Phase II—Visits During Radiation Treatment

Visit 4-9: Patients will be monitored for acute radiation toxicity including skin changes and desquamation. Patients will be questioned and examined to ensure general health and will be reassured about radiation-related side effects. Patients will turn in their food diary from the previous week and dietary counselors will review these with the patients to determine how they can continue to comply with dietary modification. At each visit, a 24hr recall of diet will be asked of the patient and compared with the diet journal to determine the self reporting accuracy. Each week during this period, patients will be counseled on their diet and given behavioral modification lessons corresponding to specific weeks in the diet (see Appendix V for worksheets). Weight will be taken at weeks 3, 5 and 7 of the diet, corresponding to weeks 1, 3 and 5 of radiation and vital signs will be performed weekly. FACT-B psychosocial assessment will be given at visit 7 along with the PROMIS cancer fatigue short form. In addition, at visit 7 (week 5 of diet) patients will have a fasting blood draw done for insulin level.

Radiation will be planned to be administered 5 days a week, Monday through Friday. Radiation is given for approximately 6-6.5 weeks or 30-33 treatments.

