6.2.4 Phase III—Post Radiation Treatment

Visit 10: Week 9 of diet, for scheduling purposes. Weight and vital signs will be measured. Patients will be monitored for acute radiation toxicity including skin changes and desquamation. Patients will turn in their food diary from the previous week and dietary counselors will review these with the patients to determine how they can continue to comply with dietary modification. A 24hr recall of diet will be asked of the patient and compared with the diet journal to determine the self-reporting accuracy. Patients will be counseled on behavioral modification for the final week of their diet (see Appendix V for worksheet). Weight and vital signs will be measured.

Visit 11: Week 10 of diet, +/- 3-5 days for scheduling purposes, last day of diet; Fasting blood draw to be done for CBC, basic metabolic panel, hemoglobin A1C, triglycerides, insulin, IGF-1, erythrocyte sedimentation rate (ESR), adiponectin, leptin and estradiol. Separately, blood will be analyzed for IRS-1, IGF-1R. Weight and vital signs will be measured. Conclusion bioimpedance and caliper measurements will be taken. Patients will be monitored for acute radiation toxicity including skin changes and desquamation. Patients will turn in their food diary from the previous week and dietary counselors will review these with the patients to determine how they can continue to comply with dietary modification. A 24hr recall of diet will be asked of the patient and compared with the diet journal to determine self-reporting accuracy. Patients will complete the FACT-B psychosocial evaluation as well as the PROMIS cancer fatigue short form.

Visit 12: 4 weeks after completion of diet. Fasting blood draw to be done for CBC, basic metabolic panel, hemoglobin A1C, triglycerides, insulin, IGF-1, erythrocyte sedimentation rate (ESR), adiponectin, leptin and estradiol. Separately, blood will be analyzed for IRS-1, IGF-1R. Weight, bioimpedance, caliper measurements and vital signs will be measured. Patients will be monitored for acute radiation toxicity including skin changes and desquamation. Patients will turn in their food diary from the last diet week. FACT-B and PROMIS cancer fatigue short form will be administered.

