6.4.1.2 Lumpectomy PTV Cavity: Total dose will be 10-16 Gy in 5-8 fractions

6.4.1.3 Total radiation dose 60-66Gy

6.4.2 Technical Factors

6.4.2.1 The patient may be treated by photon or electron radiation therapy. Fields and treatment type will be up to the discretion of the treating radiation oncologist and may include but is not limited to 3D-RT, IMRT and en face.

- 6.4.2.2 The guidelines for IMRT in this trial will conform to the policies set by the Advanced Technology Consortium (ATC) and the National Cancer Institute (NCI) http://atc.wustl.edu/home/NCI/NCI_IMRT_Guidelines.html
- 6.4.2.3 Megavoltage photon beams with energies ≥ 6 MV and megavoltage electron beams are required.

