7.3 Subject Population(s) for Analysis

All subjects enrolled in the study who completed at least 4 food diaries per week during the diet modification phase will be used for analysis.

8 Safety and Adverse Events

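### The 4-diary rule cannot be met by a 1-3 day last diet week, which most 31-33 fraction schedules produce at their minimum length, and sections 3.2 and 7.3 treat such a patient differently

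*Combined protocol and SAP*

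**What the plan says.** Four parts of the combined protocol and SAP bear on this.

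- **Length of the diet phase (section 3.2).** The phase is the whole time on the diet. It includes "a minimum of 2 weeks before the patient starts radiation therapy and a minimum of 2 weeks after completion of radiation therapy", and it is counted "regardless of whether or not the patients have exceeded the 10 weeks".
- **Radiation schedule (sections 6.2.3 and 6.4.1).** "Radiation will be planned to be administered 5 days a week, Monday through Friday". "Radiation is given for approximately 6-6.5 weeks or 30-33 treatments". The range comes from 25 whole-breast fractions plus a boost: "Total dose will be 10-16 Gy in 5-8 fractions".
- **Weekly rule (section 3.2).** Diaries are daily. A week fails if its average intake is above target, and also "if there are fewer than 4 diaries during any given week, that week will be considered as non-adherent". A patient is adherent if at least 80% of her logged events meet the target. Logged events is not defined.
- **Analysis population (section 7.3).** Only enrolled subjects who "completed at least 4 food diaries per week during the diet modification phase" are analysed.

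The last diet visit (Visit 11, section 6.2.4) is set at "Week 10 of diet, +/- 3-5 days for scheduling purposes, last day of diet". Section 5.1 allows a tolerance of 1-2 weeks around ten weeks.

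**The concern.** A block of 1, 2 or 3 days holds at most 3 daily diaries, so it cannot reach 4. If the days left over after the tenth full week are treated as a week, that week is non-adherent by construction. The number of fractions and the weekday of the start then affect a patient's adherence result, although neither has anything to do with how she ate.

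Section 7.3 adds a second problem. If it means at least 4 diaries in every week, a patient who completed every diary is left out of the analysis because her last week was short. Section 3.2 treats the same patient differently: it keeps her and scores the week as failed.

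At stake is the Phase 1 primary endpoint, the proportion of adherent patients tested against 60%. Without a written rule, someone must decide whether a short last week counts, is ignored or removes the patient, possibly after the diaries have been read.

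**Working it through.** **1. The plan's own figure.** Section 7.1 gives n = 40, 60% versus 80%, and a one-sided exact binomial test at 0.05. The smallest rejection count with P(X ≥ r | 0.60) ≤ 0.05 is r = 30, with alpha 0.035. Power is P(X ≥ 30 | n = 40, p = 0.80) = 0.839, which agrees with the stated 83%.

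**2. Length of the diet phase.** Assume exactly 14 days before and after radiation, no missed treatment days, and weeks counted from diet day 1. For n fractions starting on weekday w (Monday = 0 to Friday = 4), the calendar span of radiation is S = n + 2 × floor((n − 1 + w)/5). The diet lasts D = 14 + S + 14 days. Example: 31 fractions from a Monday give S = 31 + 2 × 6 = 43 and D = 71.

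| Fractions | Start day | D (days) | Full weeks + remainder |
|---|---|---|---|
| 30 | Mon | 68 | 9 wk + 5 d |
| 30 | Tue-Fri | 70 | 10 wk + 0 d |
| 31 | Mon-Fri | 71 | 10 wk + 1 d |
| 32 | Mon-Thu | 72 | 10 wk + 2 d |
| 32 | Fri | 74 | 10 wk + 4 d |
| 33 | Mon-Wed | 73 | 10 wk + 3 d |
| 33 | Thu-Fri | 75 | 10 wk + 5 d |

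For 31-33 fractions, 5 + 4 + 3 = 12 of 15 combinations leave 1-3 days, and 3 of 15 leave 4-5 days. Missed treatment days shift the pattern: one missed day gives a 30-fraction patient a 1-day remainder for every start day.

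**3. Effect on one patient if weeks are scored.** With 10 weeks, 80% is 8, so 2 failures are allowed. With 11 weeks, 0.8 × 11 = 8.8, so 9 are needed and again 2 failures are allowed. The short week uses one of them, so she needs 9 of her 10 full weeks. With independent weeks:

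| Weekly pass probability | P(≥ 8 of 10) | P(≥ 9 of 10) |
|---|---|---|
| 0.80 | 68% | 38% |
| 0.85 | 82% | 54% |
| 0.90 | 93% | 74% |

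**4. Effect if diary days are scored.** The remainder is 1/71 = 1.4%, 2/72 = 2.8% or 3/73 = 4.1% of the days, so the effect on adherence is small.

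**5. Illustration for Phase 1, scoring route.** The documents do not give the share f of patients affected; 25% and 50% are assumptions. Set the weekly pass rate so that P(≥ 8 of 10) = 0.80 for a 10-week patient, and let a = P(≥ 9 of 10) for an affected patient. Overall adherence is p = (1 − f) × 0.80 + f × a, and power is P(X ≥ 30 | 40, p).

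- Independent weeks: weekly pass rate 0.842 and a = 0.517. For f = 25%, p = 0.729 and power is 0.46. For f = 50%, p = 0.658 and power is 0.14.
- Beta-binomial weeks with within-patient correlation 0.5: mean weekly pass rate 0.861 and a = 0.746. For f = 25%, p = 0.787 and power is 0.78. For f = 50%, p = 0.773 and power is 0.71.

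**6. Illustration for Phase 1, exclusion route.** If 7.3 removes affected patients and the rest adhere at 80%, an assumed share of 10%, 25% or 50% leaves n = 36, 30 or 20. The rejection counts are 27, 23 and 17, and power is 0.832, 0.761 and 0.411.

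**The case against.** **The end date is not fixed.** Both 2-week periods are minimums, section 5.1 gives a tolerance and Visit 11 has a window, so a diet can end on a full week. The flowchart (6.3) stops at diet week 10 and the treatment overview (6.1) shows ten weeks of diet, so a scored eleventh week is an inference. This stands as a limit on how often the problem occurs. It does not remove it: stopping at day 70 after 31, 32 or 33 fractions from a Monday start leaves 70 − 57 = 13, 12 or 11 days after the last fraction, short of the 2-week minimum in 3.2. Those passages must be reconciled.

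**Not every 31-33 fraction patient is affected.** A reader might infer that the last week fails automatically for all of them. The calendar does not support this: 3 of 15 combinations leave 4-5 days, which can hold 4 diaries. Nor does a failed short week make a patient non-adherent by itself, since one further failure is still allowed.

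**The Visit 11 window is a weaker source.** A reader might infer that closing early, for example on day 64-66, creates more short weeks. The shortest minimum schedule is already 68 days, so such an end would break the 2-week post-radiation minimum.

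**Logged events may mean days.** Aim 1a in section 1.2 speaks of 80% of the days. That reading nearly removes the adherence effect. Against it, 3.2 declares weeks adherent or not, and 5.6 asks for a weekly reduction. The ambiguity is real, but the exclusion under 7.3 does not depend on it.

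**The two harms are alternatives.** A patient dropped under 7.3 is not also counted as non-adherent, so the losses in steps 5 and 6 must not be added. Section 7.3 could also be read as an average of 4 diaries per week, although the per-week reading is the natural one.

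**Conclusion.** The point holds in a limited form. On the minimum schedule, the stated rules leave a last block that cannot pass in 12 of 15 combinations of start day and fraction number. They can therefore hold a fully compliant patient to a stricter standard (9 of 10 full weeks instead of 8), or drop her. This needs correcting, because it affects the Phase 1 primary endpoint and because 3.2 and 7.3 contradict each other on any low-diary week.

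The adherence effect rests on two readings: that the remainder counts as a week, and that weeks are the scored unit. If days are scored, it shrinks to 1-4% of days and only the exclusion is left.

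A reader might infer that the stated 83% power is wrong. The documents do not support that: the figure reproduces, and it assumes 80% adherence on the endpoint as defined. Tying 80% to 10-week patients is a choice made for illustration. On that choice, power is about 0.46-0.78 with 25% affected and about 0.14-0.71 with 50% affected. The low ends assume independent weeks, which is doubtful for eating habits; the high ends assume a within-patient correlation of 0.5. The power may be optimistic, by an amount that cannot be fixed from the documents.

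**What to change.** Add to section 3.2: weeks are consecutive 7-day blocks from diet day 1; the scored unit is the week, and adherence means that at least 80% of scored weeks meet the target; a final block of fewer than 4 days is merged with the preceding week and not scored alone; a final block of 4-6 days is scored as a week. Bring the wording of Aim 1a in 1.2 and of 5.6 into line.

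Apply the same definition in 7.3 and reconcile it with 3.2, so that a low-diary week is scored as non-adherent and does not remove the patient from the analysis.

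One unevenness remains: a 4-day final block needs 4 diaries out of 4, while a full week needs 4 out of 7. If that is not acceptable, every partial final block can be merged in the same way.

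The cost is a few sentences, written before the diaries are scored. No new data or patients are needed, and the diet schedule does not change.

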Specific Aim 1: In a clinical trial, will investigate the ability of CR to modulate the effects of radiation in the treatment of early breast cancer. Aim 1a. Adherence will be assessed and is defined for each patient as achieving 25% reduction of her normal caloric intake (weekly average of diet journals), during at least 80% of the days during the intervention. Aim 1b. Acute skin toxicity as defined by the National Cancer Institute Common Toxicity Criteria (NCI CTCv.4 for skin reaction, pain and the occurrence of moist desquamation) will be followed to ensure noninferiority as compared with historical controls. **Specific Aim 2: Investigate measurable changes of patient characteristics along with serum markers from CR to determine a metric for evaluating this treatment in future studies.** Patient characteristics such as weight, vital signs, body fat measurements, psychosocial evaluation and outcomes will be monitored. Additionally, members of the IGF-1R-AKT pathway, and glucose and insulin in the serum, will be assessed to create a molecular signature of response to this therapy.

The innovative use of caloric restriction as a novel therapeutic option has the potential to change the biology of tumors and enhance the clinical benefit of current treatments for breast cancer. If patients are noted to be compliant, we will be able to open a larger study to determine if the combination of radiation and caloric restriction is more efficacious than radiation alone.

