4.5 Early Withdrawal of Subjects

4.5.1 When and How to Withdraw Subjects

Patients will be informed that they have the right to withdraw from the study at any time for any reason, without prejudice to their medical care. The investigator also has the right to withdraw patients from the study for any of the following reasons:

1. Intercurrent illness
2. Occurrence of an unacceptable adverse event such as a Grade ≥ 4 toxicity or $\geq 20\%$ weight
3. Missing more than 3 consecutive days of planned radiation
4. Patient request
5. Protocol violations based on the judgment of PI
6. Non-compliance
7. Administrative reasons
8. Failure to return for follow-up
9. General or specific changes in the patient's condition unacceptable for further treatment in the judgment of the investigator
10. Patients may withdraw from the study voluntarily at any time; however, the Principal Investigator reserves the right to remove patients from the study for any of the following reasons.
11. Radiation toxicity becomes too severe and the patient can no longer tolerate consecutive radiation treatments as determined by treating radiation oncologist.
12. Patients are hospitalized for another condition that is unrelated to breast cancer. Particularly admissions lasting longer than 4 days.
13. Patients develop any of the exclusionary conditions during treatments including: hepatic insufficiency, diabetes, disorders requiring corticosteroid treatment, renal failure or pregnancy.
14. Patients become sexually active and do not wish to use contraception or patients discontinue previous method of contraception and remain sexually active.

At the time of withdrawal, all study procedures outlined for the End of Study visit should be completed. The primary reason for a patient's withdrawal from the study is to be recorded in the source documents.

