7.2 Statistical Methods

Primary endpoint (adherence). We will compute the proportion of patients who are adherent to the diet restriction (as defined in section 3.2), along with a 95% exact confidence interval. We will also use an exact binomial test (with a one-sided alpha of 0.05) to test whether adherence is greater than 60%.

Aim 1b. We will compute the proportion of patients with toxicity, along with a 95% exact confidence interval. Our institution's historical toxicity rate among similar patients is about 80% and we aim to prove that the dietary intervention is non-inferior with an absolute margin of 10%, using an exact binomial test. With a total sample size of 90 and assuming that true toxicity will be 80% or lower, we have 82% power (with one-sided alpha of 0.05).

Secondary endpoints. The change in body fat measurement between baseline and the end of the study will be analyzed via a paired t-test. Weight changes over time will be assessed by modeling BMI as a function of time (baseline, diet weeks 1, 3, 5, 7, and 10) via mixed-effects regression. The patterns of change over time in vital signs, insulin and other clinical labs, serum markers, and psycho-social outcomes (FACT-B) will also be analyzed similarly. If some of these measures are skewed, we will transform them (e.g., log) before the analyses. Finally, local recurrence, distant metastases, progression free survival, and overall survival will be analyzed via survival methods, specifically the Kaplan-Meier method and the logrank test. If sufficient events occur, we may assess the impact of various patient and clinical/treatment variables on these outcomes via Cox proportional hazards regression.

Local recurrence, progression free survival, distant metastases and overall survival will be assessed and compared with historic controls using the Kaplan Meier method. Local recurrence, progression free survival, distant metastases and overall survival will be measured from the date of study enrollment to time of event.

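### Phase 1 adherence: section 3.2 scores an under-logged week as a failure, section 7.3 read literally removes the patient, and the 80% threshold has no defined denominator

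*Combined protocol and SAP*

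**What the plan says.** Section 3.2 averages daily intake over each diet week and compares it with the patient's target. It adds that "if there are fewer than 4 diaries during any given week, that week will be considered as non-adherent". Overall adherence is then "defined as at least 80% of all logged events meeting the diet restriction target". The term *logged events* also appears in the Study Summary, 2.1 and 5.6, and is defined in none of them.

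Section 7.2 refers to 3.2 for the definition, computes the proportion of adherent patients and tests it against 60% with a one-sided exact binomial test at 0.05. Section 7.1 gives 83% power for 40 patients if true adherence is 80%.

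Section 7.3 is the only statement of an analysis population. It uses enrolled subjects "who completed at least 4 food diaries per week during the diet modification phase will be used for analysis".

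Three other places bear on the denominator:

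- Specific Aim 1a in 1.2 describes adherence as "25% reduction of her normal caloric intake (weekly average of diet journals), during at least 80% of the days during the intervention", with no minimum number of diaries.
- Section 3.2 also states: "The diet phase will be defined as the entire length that a patient is on the calorically restricted diet".
- Section 4.5.1 says "The investigator also has the right to withdraw patients from the study for any of the following reasons" and lists non-compliance as item 6. Section 4.5.2 keeps data collected before withdrawal in the analysis for patients who decline further follow-up.

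**The concern.** The 3.2 rule makes sense only if a patient with an under-logged week is analysed. Read literally, 7.3 excludes her after one such week, so the rule never applies to anyone analysed. A softer reading of 7.3, at least four diaries per week on average, would leave the rule some effect. The text does not say which is meant.

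In a feasibility trial, failing to keep the diary is part of the outcome. Removing those patients conditions the adherence estimate on part of what it is meant to measure. Because an under-logged week is itself a failed week under 3.2, the removal can favour a finding of feasibility even if under-loggers diet as well as everyone else.

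The undefined denominator adds a second gap. If an under-logged week is not a logged event, it drops out of the 80% instead of counting against it. A third gap is early withdrawal: no section says whether weeks after withdrawal count.

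At stake is the Phase 1 conclusion. Section 1.2 says: "If patients are noted to be compliant, we will be able to open a larger study". The plan states no adherence gate for Phase 2, so no stopping decision is affected.

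**Working it through.** **Inputs from the documents.** n = 40, null adherence 0.60, alternative 0.80, one-sided exact binomial, alpha 0.05 (7.1, 7.2); diet phase of at least 10 weeks and a four-diary minimum per week (3.2). The documents give no rate of under-logging or exclusion, so every such rate below is an assumption.

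**1. The plan's own figure.** P(X ≥ r | n, p) = Σ C(n,x) pˣ(1−p)ⁿ⁻ˣ, summed over x ≥ r. The smallest r with P(X ≥ r | 40, 0.60) ≤ 0.05 is 30. The actual alpha is 0.0352 and power at 0.80 is 0.839. The stated 83% is confirmed, for 40 patients analysed.

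**2. One patient, several answers.** Take ten weeks: seven with seven diaries and on target, three with three diaries.

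| Reading | Result |
|---|---|
| All weeks count | 7/10 = 70%, non-adherent |
| Under-logged weeks are not logged events | 7/7 = 100%, adherent |
| 7.3 literally | excluded |
| 7.3 as an average: (7×7 + 3×3)/10 = 5.8 diaries per week | kept |

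A patient withdrawn after five weeks, four of them adherent, scores 4/5 = 80% (adherent) if her diet phase ends there, or 4/10 = 40% if ten weeks count.

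**3. Same data, different trial result.** Suppose 27 patients are adherent and under-logged failures are dropped.

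| Dropped | Adherent/analysed | P(X ≥ 27 given n, 0.60) | Criterion |
|---|---|---|---|
| 0 | 27/40 | 0.211 | not met |
| 3 | 27/37 | 0.072 | not met |
| 4 | 27/36 | 0.045 | met |

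**4. Chance of declaring success when true adherence among all enrolled is 60%.** Let K ~ Bin(40, e) patients be dropped, a share s of them adherent under 3.2. Adherence among those kept is (0.60 − s·e)/(1 − e), and the test uses the cut-off for n = 40 − K. For example, e = 0.10 and s = 0 gives 0.60/0.90 = 0.667 among those kept.

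| Share s of dropped who are adherent | e = 5% | e = 10% | e = 15% |
|---|---|---|---|
| 0 (worst case) | 8.0% | 15.9% | 29.3% |
| 0.5 | 4.1% | 4.7% | 5.4% |
| 0.6 (break-even) | 3.6% | 3.5% | 3.5% |
| 1 | 2.0% | 1.0% | 0.4% |

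With all 40 counted it is 3.5%.

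**5. A model that does not fix s.** Assume ten independent weeks and identical patients. Each week is under-logged with probability u, otherwise on target with probability a; a patient is adherent with at least 8 of 10 good weeks. Setting (1 − u)·a = 0.7745 makes adherence among all enrolled exactly 60%. Literal 7.3 drops 1 − (1 − u)¹⁰ of patients, and adherence among those kept is P(Bin(10, a) ≥ 8).

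| u | Dropped | Adherent among kept | Adherent among dropped | Chance of success |
|---|---|---|---|---|
| 1% | 9.6% | 62.4% | 37.4% | 6.4% |
| 3% | 26.3% | 67.3% | 39.5% | 15.0% |
| 5% | 40.1% | 72.3% | 41.6% | 25.8% |

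**6. Power, as a separate scenario.** If adherence is 80% among those retained, power is 0.785 at n = 38, 0.832 at 36, 0.773 at 34, 0.800 at 33 and 0.698 at 32; it moves in a saw-tooth. In the step 4 model with 80% overall adherence, power is 82/80/77% at e = 5/10/15% if those dropped are also 80% adherent, and 95/99/>99% if they are all failures. Inflated error and lost power therefore do not occur together.

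**The case against.** The conflict between 3.2 and a literal 7.3 is hard to dispute; the case on the other side concerns its reach.

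- **Denominator.** The sentence just before the 80% threshold calls an under-logged week non-adherent, which matters only if that week stays in the denominator. The 7/7 reading is therefore strained. This stands: 7/10 is the more natural reading. But the wording does not secure it, and 7.3 removes the patient anyway.
- **Days.** Aim 1a is background text that itself mentions a weekly average, and 7.2 points to 3.2. This stands too: *days* is a mismatch to tidy. The conflict over under-logged weeks remains if everything is read weekly.
- **Withdrawal.** Section 3.2 speaks of adherence over the whole study and of at least ten weeks on the diet, which leans against 4/5. It does not settle the matter, and scoring later weeks as failures is a choice of estimand.
- **Size.** The 8/16/29% figures need every dropped patient to be a failure, although 3.2 tolerates two failed weeks in ten. With half of them adherent the error stays near 5%. The larger week-model figures need 26% or 40% of patients dropped, and clustering of under-logging in a few patients would reduce that. All fair: the bias is possible, not demonstrated.
- **Consequence.** This is a single-arm pilot with no gate on adherence. True, but it is the primary Phase 1 test.

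**Conclusion.** The concern holds and should be corrected before analysis. Followed literally, the plan removes the patients to whom its own failure rule applies and then tests adherence among the rest. This is a conflict between stated rules on a primary endpoint, not a missing detail.

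Its size cannot be fixed from the documents. At 60% true adherence and 5 to 15% of patients dropped, the chance of a false success ranges from 0.4% to 29%, depending on how many of those dropped are adherent. With under-logging unrelated to dietary success within a week, it is 6 to 26% for 1 to 5% of weeks under-logged, given independent weeks and identical patients. The stated power is correct for 40 analysed patients.

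The undefined *logged events*, the use of days in Aim 1a and the scoring of withdrawals are lesser points that the same edit should settle.

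**What to change.** 1. **Week rule.** Use 3.2's test throughout: a week is adherent if it has at least four diaries and its mean daily intake is at or below the 3.2 target.
2. **Patient rule.** A patient is adherent if at least 80% of all her diet-phase weeks are adherent, with under-logged and unlogged weeks counted as non-adherent. Replace *logged events* (Study Summary, 2.1, 3.2, 5.6) and *days* (Aim 1a) with this rule.
3. **Population.** Amend 7.3 so that the adherence analysis includes every enrolled patient who starts the diet, with the four-diary restriction as a sensitivity analysis. Say how enrolled patients who never start are handled, since the 3.5% and 83% figures assume 40 analysed. As 7.3 is the only population stated, also say which one applies to toxicity.
4. **Withdrawal.** State in advance how weeks after early withdrawal and a partial last week count. Scoring post-withdrawal weeks as non-adherent suits a feasibility question, but should be declared as an estimand choice.

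The cost is protocol and SAP wording, with no new data, visits or patients. The downside is that observed adherence may be lower.
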